4. HYPOTHESES, SAMPLE SIZE AND DECISION RULES

4.1. Statistical Hypotheses

No formal testing of hypotheses will be conducted in this study.

4.2. Statistical Decision Rules

The following table shows the probability of escalating to the next dose level for a range of underlying true dose limiting toxicity (DLT) rates. For example, for a DLT that occurs in 10% of patients, there is a greater than 90% probability of escalating. Conversely, for a DLT that occurs with a rate of 70%, the probability of escalating is 3%. It is assumed that dose escalation occurs with either 0/3 or 1/6 patients with DLTs.

Table 1. Probability of Escalating Dose

True underlying DLT rate	10%	20%	30%	40%	50%	60%	70%	80%	90%
Probability of escalating dose	0.91	0.71	0.49	0.31	0.17	0.08	0.03	0.009	0.001

Probabilities of testing sequential doses can be calculated as the 3+3 escalation rules are predefined. For example the probability of escalating to a third dose level is 0.64 under the assumption that DLTs occur in 10% and 20% of patients respectively in the first dose and the second dose. The probability of escalating to a third dose is only 0.35 if DLTs occur in 20% and 30% of patients respectively in the first dose and the second dose tested.

4.3. Sample Size Determination

The exact sample size of the 3+3 designs in the Phase 1 Part A (Dose Escalation) cannot be pre-specified because of the dynamic feature of the design. The number of patients to be enrolled in the study will depend upon the observed safety profile, which will determine the number of patients at each dose level (eg, 3 or 6) and the number of dose levels explored.

Typically, at least 3 patients will be treated at each regimen dose level. Dose cohorts with an acceptable safety profile (0/3 or 1/6 patients with DLTs) may be expanded up to N=15 to further assess safety, immune response, pharmacokinetics, and pharmacodynamics.

Decisions to enroll additional patients at dose levels already cleared for safety will be based on clinical judgment of the investigators and the sponsor considering all evaluable safety, immunoresponse, and/or pharmacodynamics data.

The estimated sample size for Part A would be 24-48 patients and will be dependent on the safety profile observed.

The sample size for Cohort 1B (AdC68 + pDNA + tremelimumab 80 mg SC for BCR patients who had no prior therapy) was determined clinically rather than statistically. Twenty patients were enrolled in that cohort to provide preliminary efficacy, safety, PK and biomarker data for this regimen.

For Cohort 3B (AdC + pDNC + tremelimumab 80 mg SC + PF-0689159 300 mg SC for patients with mCRPC whose disease has progressed despite novel hormonal treatment), 18 patients

were enrolled. The main efficacy endpoint for this cohort will be objective response rate (ORR) based on RECIST version 1.1, the key supportive efficacy endpoint will be radiographic progression-free survival (rPFS). There are no hypothesis tests for these endpoints. Bayesian approach may be used to evaluate the efficacy data. For example, Bayesian approach with a non-informative Jeffery's prior beta (0.5,0.5) will be used to calculate the posterior probability the ORR of the study treatment exceeds various ORR thresholds of interest in the end of the study.

For Cohort 5B (AdC68 + pDNA + tremelimumab 80 mg SC + PF-0689159 130 mg SC. for BCR patients who had no prior therapy), the sample size was determined clinically rather than statistically. Fifteen patients were enrolled in that cohort to provide preliminary efficacy, safety, PK and biomarker data for the regimen.

5. ANALYSIS SETS

5.1. Safety Analysis Set

The safety analysis set includes all enrolled patients who receive at least one dose of one of the components of the regimen.

5.2. Full Analysis Set

The full analysis set includes all enrolled patients.

5.3. Per-Protocol Analysis Set

The per protocol (PP) analysis set includes all enrolled patients (for each indication) who receive at least one dose of the assigned regimen components administered on Cycle 1 Day 1 of study medication and who do not have major protocol deviations during the 28 days after the first vaccination. Major protocol deviations will be determined before data base release.

5.4. Modified Intent-to-Treat Analysis Set

The modified Intention-to-Treat (mITT) is defined as all enrolled patients who received at least one dose of all assigned regimen components administered on Cycle 1 Day 1 of treatment.

5.5. Pharmacodynamics Analysis Set

The pharmacodynamics analysis set will be based on the mITT population. A patient must have at least 1 valid and determinate assay result related to the proposed analysis. Patients who have no valid and determinate assay result related to any proposed analysis will be excluded from the pharmacodynamics analysis set.

5.6. Evaluable Population

As a consequence of its mechanisms of action, PrCa VBIR may require time after administration to induce a prostate cancer-specific immune response and subsequent tumor response. Therefore, tumors in patients treated with cancer vaccines may show early progression followed by subsequent response, therefore, supportive analysis populations may be based on the evaluable population (EP) which will consist of all patients in the mITT

population who have been dosed through Cycle 1 Day 57, Day 85 or Day 113 (Day 113 is Cycle 2 Day 1). To implement this, 3 sub-populations will be created: EP C1D57, EP C1D85, and EP C2D1. EP C1D57 will include all patients who have received all assigned doses at least until C1D57. EP C1D85 and EP C2D1 are defined in the same manner.

Additionally, tumor response and PD analyses may be repeated in the mITT population in patients who have no major protocol deviations during the first and second treatment cycle.

5.7. Treatment Misallocations

For patients with errors in treatment allocation the following approach will be followed:

If a patient was:

- Enrolled but not treated, then they will be reported under their enrolled treatment group for demographic analyses only. These patients will be excluded from the immunogenicity, efficacy and safety analyses as the actual treatment is missing.
- Enrolled but took incorrect treatment, then they will be reported under their enrolled treatment group for efficacy analyses based on mITT, excluded from analyses based on PP, but will be reported under the treatment they actually received for all safety, PK, immune responses, and anti-tremelimumab or anti-PF-0680159 immunogenicity analyses.

5.8. Protocol Deviations

Major protocol deviations will be determined on an ongoing basis per medical data review. Any major protocol deviation will prevent the patient from being included in the per-protocol population.

A full list of major protocol deviations will be compiled prior to database closure. Once the final list of major protocol deviations is determined the per-protocol population flag will be updated.

6. ENDPOINTS AND COVARIATES

6.1. Part A Primary Endpoint

- *Incidence and grade of treatment-emergent adverse events including DLTs as graded by National Cancer Institute Common Terminology Criteria for Adverse Events (NCI CTCAE version 4.03).*

6.2. Part A Secondary Endpoint

- *Immune response including T cells specific to the three selected prostate cancer tumor-antigens. T cell immune response will be determined as the frequency of IFN- γ spot forming cells (SFC)/million peripheral blood mononuclear cells (PBMC) in response to Prostate-Specific Membrane Antigen (PSMA), Prostate Stem Cell Antigen (PSCA) and Prostate-Specific Antigen (PSA) as measured in the IFN- γ ELISPOT assay. For analysis in the IFN- γ ELISPOT assay, the PSMA antigen will*

[figure not shown]
be divided into three sub regions (peptide pools) for which the IFN- γ spot forming cells/million PBMCs will be reported separately (ie, 5 reported values) or by antigen (3 PSMA summed) or all pooled. The PSCA and PSA assays will each be analyzed as a single antigen (ie, 1 reported value for each antigen). ELISPOT assay reported variables, by the Lab, are specified and listed in the respective CSAP document.

- *Antibody response specific to the PSMA antigen* (Geometric Means and Seroconversion): will be determined as the titer (U/mL) of serum IgG antibodies elicited against the PSMA antigen as measured in the Luminex-based assay.
- *Laboratory abnormalities as characterized by type, frequency, severity (as graded by NCI CTCAE v 4.03) and timing.*
- *Tremelimumab single-dose PK parameters, including the maximum concentration (C_{max}), time to maximum concentration (T_{max}), and area under the concentration versus time curve (AUC) from time zero to the last quantifiable time point prior to the second tremelimumab dose (AUC_{last}) and if data permit, AUC from time zero extrapolated to infinity (AUC_{0-inf}); and trough concentrations after multiple dosing (C_{trough}).*
- *PF-06801591 single-dose PK parameters, including C_{max} , T_{max} , AUC_{last} , and if data permit, AUC_{inf} , and C_{trough} after multiple dosing.*
- *Incidence and titers of ADA and neutralizing antibodies against tremelimumab.*
- *Incidence and titers of ADA and neutralizing antibodies against PF-06801591.*

6.3. Part A Exploratory Endpoints

- *Objective tumor response, as assessed using the Response Evaluation Criteria in Solid Tumor (RECIST) version 1.1 by calculating the Objective Response Rate (ORR) and radiographic Progression-Free Survival (PFS).*
- *Antitumor response based on total measurable tumor burden as assessed by the Immune-Related Response Criteria (irRECIST) and irPFS.*
- *Bone outcome according to Prostate Cancer Working Group 3 (PCWG3) criteria.*

[figure not shown]
6.4. Part B Primary Endpoint

- *Incidence and grade of treatment-emergent adverse events including DLTs as graded by National Cancer Institute Common Terminology Criteria for Adverse Events (NCI CTCAE version 4.03).*

6.5. Part B Secondary Endpoint

- *For Cohort 3B: Objective response rate (ORR) and duration of response, as assessed using the Response Evaluation Criteria in Solid Tumors (RECIST) version 1.1.*
- *For Cohort 3B: Antitumor response and tumor control duration based on total measurable tumor burden as assessed by the Immune-Related Response Criteria Derived from RECIST 1.1 (irRECIST).*
- *For Cohort 3B: Bone outcome according to Prostate Cancer Working Group 3 (PCWG3) criteria.*
- *For Cohort 3B: Radiographic Progression-Free Survival (rPFS) by RECIST 1.1, irRECIST and PCWG3 Criteria in participants with mCRPC.*
- *PSA-50 response rate and duration of response.*
- *Baseline and changes from baseline for PSA, PSA velocity, PSA slope and PSA doubling time (PSADT).*
- *Trough concentrations after multiple dosing (C_{trough}).*
- *C_{trough} after multiple dosing.*
- *Incidence and titers of ADA and neutralizing antibodies against tremelimumab.*
- *Incidence and titers of ADA and neutralizing antibodies against PF-06801591.*

CCI

- 
- 
- 
- 
- 
- 
- 
- 

6.7. Covariates

Analyses of immune response and analyses of pharmacodynamic parameters may be adjusted (or stratified) by demographic and prognostic variables (eg, age, Gleason score, baseline PSA, baseline PSADT etc).

7. HANDLING OF MISSING VALUES

CCI

All the safety, immune responses, pharmacokinetic, pharmacodynamics, and immunogenicity analyses and summaries will be based on data as observed and no explicit imputation will be applied.

7.2. Immune Responses Lower Limit of Quantitation

Titers below the assay detection limit will be assigned a value of one-half that limit.

7.3. Pharmacokinetic Concentrations and Parameters

Drug concentrations below the limit of quantification

In all data presentations (except listings), drug concentrations below the limit of quantification (BLQ) will be set to zero. In the listings BLQ values will be reported as “<LLQ”, where LLQ will be replaced with the value for the lower limit of quantification.

Deviations, missing concentrations and anomalous values

Patients who experience events that may affect their PK (eg, incomplete dosing) may be excluded from the PK analysis.

In summary tables and plots of mean profiles of PK, statistics will be calculated having set concentrations to missing if 1 of the following cases is true:

1. A concentration has been collected as ND (ie, not done) or NS (ie, no sample);
2. A deviation in sampling time is of sufficient concern or a concentration has been flagged anomalous by the PK analyst.

Note that summary statistics will not be presented at a particular time point if more than 50% of the data are missing.

An anomalous concentration value is one that, after verification of bioanalytical validity, is grossly inconsistent with other concentration data from the same individual or from other patients. For example, a BLQ concentration that is between quantifiable values from the same dose is considered as anomalous. Anomalous concentration values may be excluded from PK analysis at the discretion of the PK analyst.

Pharmacokinetic parameters

Actual PK sampling times will be used in the derivation of PK parameters.

If a PK parameter cannot be derived from a patient's concentration data, the parameter will be coded as NC (ie not calculated).

In summary tables, statistics will be calculated by setting NC values to missing; and statistics will not be presented for a particular treatment if more than 50% of the data are NC. For statistical analyses (ie analysis of variance), PK parameters coded as NC will also be set to missing.

7.4. Efficacy Data

For the time-to-event endpoints, the missing data handling method will be censoring. Censoring rules for time-to-event endpoints are detailed in [Appendix 10.3.](#)

8. STATISTICAL METHODOLOGY AND STATISTICAL ANALYSES

In general, all continuous endpoints will be summarized descriptively by cohort. If data are categorical then the standard contingency tables with counts and percent by group will be displayed.

8.1. Statistical Analyses

8.1.1. Baseline Evaluations

The baseline evaluation summaries and listings will display patient demographics, including age and performance status, PSA and Gleason score at the time of diagnosis. Details and dates of prior hormonal and nonhormonal therapies should be displayed, along with additional PSA measurements that can be used to estimate PSA doubling times (PSADT). Evaluable data on screened, but not enrolled patients, will be presented as listings.

8.1.2. Safety Analysis

The main analyses of DLTs will be based on the Per Protocol analysis set. Patients not meeting the criteria for inclusion in the Per Protocol Analysis set (ie, not evaluable for assessment of DLTs) will be replaced. Summaries and analyses of other safety parameters will include all patients in the Safety Analysis Set. Note only the safety data before the start of any new anti-cancer systemic therapy will be included in safety analysis.

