## **8.2. Reporting Period**

For SAEs, the active reporting period to Pfizer or its designated representative begins from the time that the patient provides informed consent, which is obtained prior to the patient's participation in the study, ie, prior to undergoing any study-related procedure and/or receiving investigational product, through and including the 6 month follow-up period. SAEs occurring to a patient after the active reporting period has ended should be reported to the sponsor if the investigator becomes aware of them; at a minimum, all SAEs that the investigator believes have at least a reasonable possibility of being related to investigational product are to be reported to the sponsor.

AEs (serious and non-serious) should be recorded on the CRF from the time the patient has taken at least 1 dose of investigational product through the patient's last visit.

If a patient begins a new anticancer therapy, the AE reporting period for non-serious AEs ends at the time the new treatment is started. Death must be reported if it occurs during the SAE reporting period after the last dose of investigational product, irrespective of any intervening treatment.

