### 9.5.1. Analysis of Primary Endpoint

**Dose Limiting Toxicity (DLT)** is the primary endpoint of the dose escalation (Part A). The occurrence of DLTs observed in the dosing cohorts will govern the dose escalation as described in [Section 3.1.1 STUDY DESIGN](#). The properties of the statistical methods for the analyses of DLTs are described in section [Statistical Methods and Properties](#). Adverse Events constituting DLTs will be listed per dose level. The per-protocol population will be used for the DLT evaluation. A patient who had a major protocol deviation may be excluded from the per-protocol population and hence will be replaced for the DLT evaluation but will still be included in the safety population for the general safety evaluation.

**Adverse Events (AEs)** will be graded by the investigator according to the CTCAE version 4.03 and coded using the Medical Dictionary for Regulatory Activities (MedDRA). The focus of AE summaries will be on Treatment-Emergent Adverse Events, those with initial onset or increasing in severity after the first dose of study treatment. The number and percentage of patients who experienced any AE, SAE, treatment related AE, and treatment related SAE will be summarized according to worst toxicity grades. The summaries will present AEs both on the entire study period by dose and by cycle.

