8.1.2.1. Analysis of Primary Endpoint

DLT is a primary endpoint of the study. The properties of the statistical methods for the analyses of DLTs are described in Section 4. Adverse events constituting DLTs are detailed in Section 3.2 of the study protocol. Adverse events and adverse events constituting DLTs will be listed per dose level (ie, by cohort). A binary variable will be created at the patient level to indicate whether or not a patient has experienced any of the adverse events that are considered DLT. If required, a summary table will be created by cohort to present number and percentage of patients experiencing DLT and each specific adverse event constituting DLT.

Adverse Events (AEs) will be graded by the investigator according to the CTCAE version 4.03 and coded using the Medical Dictionary for Regulatory Activities (MedDRA). The focus of AE summaries will be on Treatment Emergent Adverse Events, those with initial onset or increasing in severity after the first dose of study treatment and before the start of any new anti-cancer systemic therapy. The number and percentage of patients who experienced any AE, SAE, treatment related AE, and treatment related SAE will be summarized. The summaries will present AEs both on the entire study period by dose (i.e., by cohort) and by cycle. The number and percentage of patients who discontinued from study medications due to AE or discontinued from the study due to AEs will also be presented.

AE, SAE, treatment related AE, treatment related SAE will be presented by system organ class and preferred term for each cohort. Severity summary tables will also be presented where AE, SAE, treatment related AE, and treatment related SAE will be presented for each cohort by system organ class and preferred term according to the worst toxicity grade.

Treatment related AE in this study refers to those adverse events that are determined by investigator as related to either adenovirus, or plasmid DNA, or tremelimumab, or PF-06801591. If deemed necessary, further summary of component-related AE may be presented.

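### The SAP drops SAEs, treatment-related SAEs and deaths after new systemic anticancer therapy from the safety tables, although the protocol ends reporting at that point only for non-serious AEs

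*SAP*

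**What the plan says.** SAP 8.1.2 sets one rule for all safety analysis: "Note only the safety data before the start of any new anti-cancer systemic therapy will be included in safety analysis". SAP 8.1.2.1 then defines treatment-emergent events as those starting or worsening "after the first dose of study treatment and before the start of any new anti-cancer systemic therapy". It continues: "The number and percentage of patients who experienced any AE, SAE, treatment related AE, and treatment related SAE will be summarized". The serious and related classes get no window of their own, and the readable SAP text contains no exception for them or for deaths.

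The protocol treats the classes differently. Under 8.2, once a new anticancer therapy begins, "the AE reporting period for non-serious AEs ends at the time the new treatment is started". SAE reporting opens at consent, ahead of any study procedure or of "receiving investigational product, through and including the 6 month follow-up period", and nothing in 8.2 shortens that period when therapy changes. Deaths within it must be reported whatever treatment has come between. Section 8.2 also asks for serious and non-serious AEs to be recorded on the CRF from first dose to last visit.

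Protocol 9.5.1 defines treatment-emergent events as "those with initial onset or increasing in severity after the first dose of study treatment" and gives no end at new therapy.

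**The concern.** Incidence and grade of treatment-emergent AEs is the primary endpoint in both parts (protocol 2.2 and 2.3), and the SAE tables are part of its analysis. Under the SAP as written, the sponsor would hold SAEs that its own tables omit, including events the investigator attributes to study treatment and fatal events.

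The situation is foreseeable. Protocol 3.1 continues treatment until progression, refusal or unacceptable toxicity, and 6.3 follows participants for 6 months afterwards. Some can be expected to start another anticancer therapy in that time. What is at stake is the accuracy of the reported SAE and related-SAE rates in cohorts of 15 to 20.

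**Working it through.** The plan states no figure for this point, so there is none to reproduce. The check is a comparison of the texts, followed by simple conditional arithmetic.

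**Step 1. What happens to each kind of event after new therapy starts**

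| Event, with onset after first dose | Protocol 8.2 | SAP 8.1.2 and 8.1.2.1 |
|---|---|---|
| Non-serious AE after new systemic therapy | Reporting period has ended | Excluded |
| SAE, unrelated, after new systemic therapy, within the 6-month follow-up | Reported | Excluded |
| SAE, related, same window | Reported | Excluded |
| Death, same window | Reported despite intervening treatment | Excluded |
| Non-serious AE after new non-systemic therapy | Reporting period has ended | Not excluded |

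The documents agree in the first row. In the next three the SAP removes what the protocol collects. The last row is a smaller mismatch in the other direction: the SAP trigger is a new *systemic* therapy, while protocol 8.2 refers to any new anticancer therapy.

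**Step 2. Does other text supply the missing exception?**

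- The AE footnote in the Schedule of Activities (footnote 26 in the Part B table, repeated in the other schedules) lets general AE follow-up end before 6 months if another anticancer therapy starts. Its next sentence gives SAEs their own period through the 6-month follow-up, so it does not support the SAP cut for SAEs.
- SAP 8.1.2.1 says that AE summaries *focus* on treatment-emergent events, which is softer wording. The note in 8.1.2 says *only* and covers all safety analysis.
- SAP 8.1.2.2 adds splits by cohort, cycle and period, but no different window for serious events.

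**Step 3. Size if it happens**

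The inputs are the treated cohort sizes in protocol 3.1.2: 18 in 3B, 15 in 5B and 20 in 1B. If k participants in a cohort of n have their only SAE after new therapy, the reported proportion with any SAE falls by k/n. With k = 1:

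- 3B: 1/18 = 5.6 percentage points
- 5B: 1/15 = 6.7 percentage points
- 1B: 1/20 = 5.0 percentage points

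Cohort 1B received no PF-06801591, so it lies outside the Part B primary objective as worded, but the same SAP text governs its tables. The same drop applies to the related-SAE rate if the lost event is the participant's only related SAE. If the participant also had an SAE before the switch, the any-SAE rate does not move, but the preferred-term and worst-grade rows may.

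**The case against.** The best defence is that reporting and analysis are separate matters. Protocol 8.2 tells sites what to report, and the SAP says what is tabulated. Protocol Section 9 allows the SAP to modify the planned analyses, and 9.5.1 gives no end to the treatment-emergent window, so the SAP may be filling a gap. In an open-label, non-randomised study with no hypothesis tests, it is defensible to stop attributing events once another drug has started. Retained events may indeed come from the new therapy or from the disease: protocol 8.6 counts fatal progression as a grade 5 SAE. Protocol 5.7.2 bars other anti-tumour treatment during study treatment, so the affected events are essentially post-treatment ones.

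Most of this stands. It justifies showing a version with the cut. It does not justify showing only that version, because an SAE that the investigator attributes to study treatment should not vanish from the related-SAE table because another therapy had begun.

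A reader might infer more than the documents support:

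- *That the SAP contradicts itself on the period covered.* SAP 8.1.2.1 says "The summaries will present AEs both on the entire study period by dose (i.e., by cohort) and by cycle", and protocol 9.5.1 has nearly the same sentence, "The summaries will present AEs both on the entire study period by dose and by cycle". In both, the phrase is paired with a per-cycle display and reads as overall versus by cycle. Protocol 9.5.2 uses the same pairing for laboratory tests.
- *That the protocol commits to tabulating late toxicity after later therapies.* The mention of late-onset toxicity in 1.6.4 describes a completed dose-selection review. The list in 6.4.2 concerns leaving follow-up and says nothing about analysis windows.
- *That the RP2D decision is compromised.* Protocol 3.5 rests it on all the clinical evidence, and post-switch SAEs still reach the sponsor.
- *That an amendment was required and omitted.* Section 9 asks for one only if the change to the primary endpoint or its analysis is major, which is a matter of judgement.

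**Conclusion.** The concern holds as a mismatch between what the protocol collects and what the SAP tabulates. Followed literally, the SAP leaves SAEs, treatment-related SAEs and deaths after new systemic therapy out of the primary-endpoint summaries, and it narrows the treatment-emergent definition in protocol 9.5.1.

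The effect is 5.0 to 6.7 percentage points per cohort for each participant whose only SAE is lost. This assumes that all treated participants are in the denominator and that the event falls after the switch but within the 6-month follow-up. The documents give neither the frequency of new therapy in follow-up nor the number of SAEs after it, so the expected understatement cannot be calculated.

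The harm is confined to the reported rates. The 28-day DLT assessment and ongoing safety surveillance are unaffected, and the events are still collected. The point should be fixed, but it does not call the conduct of the study into question.

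**What to change.** 1. In SAP 8.1.2, limit the exclusion to non-serious AEs. The present note also covers laboratory and ECG data, so state separately what applies to those.
2. Keep the tables with the cut, labelled as such. Add a by-cohort summary of SAEs, treatment-related SAEs and deaths over the full protocol 8.2 period, regardless of new therapy. Flag events with onset after new therapy and identify fatal disease progression.
3. Use one treatment-emergent definition in SAP 8.1.2.1 and protocol 9.5.1, and one trigger, either new anticancer therapy or new systemic anticancer therapy, in the SAP and protocol 8.2.

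The cost is wording in both documents, a flag, and a few extra tables or listings. No new data collection is needed, because protocol 8.2 already requires SAE reporting in this window. Some retained events will be due to the next therapy or to disease, which the flag and the tables with the cut make visible. Capture after a switch may also be incomplete, since the schedule footnote lets general AE follow-up stop; the new summary should say so.
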